7.8. Definition of End of Study

The ending of the study is the date of the final MR imaging assessment of the last participant.

8. INTERVENTIONS (IF APPLICABLE)

8.1 DW-MR imaging scans

MRI scans will be performed in a 60-minute protocol on the 1.5T Avanto MRI scanner (Siemens, Germany) installed at OCMR. Scans will include: localizer images, high-resolution 3D imaging of the pelvis and lumbar spine, diffusion-weighted MRI imaging following the method described for use in myeloma patients by Giles *et al*, 2015; Giles *et al*, 2014; Pawlyn *et al*, 2016), and an experimental bone density quantification MR method based on published techniques (Evans *et al*, 2014; Rafferty *et al*, 2016), using software from Osteotronix Ltd, in the pelvis and two sites in the lumbar spine.

8.2 DXA scans

DXA scans will be performed in a 1 hour protocol on the DXA scanner installed at the NOC. Scans will include: body composition, bone mineral density measured at the Lumbar spine (L1-4), hip, whole body and Instant Vertebral Assessment.

9. SAFETY REPORTING

9.1. Definition of Serious Adverse Events

A serious adverse event is any untoward medical occurrence that:

- results in death
- is life-threatening
- requires inpatient hospitalisation or prolongation of existing hospitalisation
- results in persistent or significant disability/incapacity
- consists of a congenital anomaly or birth defect.

Other 'important medical events' may also be considered serious if they jeopardise the participant or require an intervention to prevent one of the above consequences.

NOTE: The term "life-threatening" in the definition of "serious" refers to an event in which the participant was at risk of death at the time of the event; it does not refer to an event that hypothetically might have caused death if it were more severe.

9.2. Reporting Procedures for Serious Adverse Events

A serious adverse event (SAE) occurring to a participant should be reported to the REC that gave a favourable opinion of the study where in the opinion of the Chief Investigator the event was 'related' (resulted from administration of any of the research procedures) and 'unexpected' in relation to those procedures. Reports of related and unexpected SAEs should be submitted within 15 working days of the Chief Investigator becoming aware of the event, using the NRES report of serious adverse event form (see IRAS/NRES/HRA website).

10. STATISTICS AND ANALYSIS

10.1. Description of Statistical Methods

The primary outcome of this study is the ADC in patients with and without a complete/very good partial response to therapy at follow-up. It is estimated that for group 1, between baseline and follow-up, 85% of individuals will reduce their myeloma burden from 40% to 10% or less compared with 15% who will achieve a partial response (a ratio of 0.15).

A previous study in a similar population the median ADC score improved from 0.79 (IQR 0.66 to 1.26) to 1.5 (IQR 0.88 to 1.83) in those with a complete/very good partial response compared with 0.66 (IQR 0.52 to 0.87) to 0.75 (0.51 to 1.27) in those with a partial response [Latifoltojar BJH 2016].

To detect a similar difference in this cohort with an ADC in complete/ very good partial response of 1.5 at follow-up vs. 0.75 in those with a partial response, a conservative estimated SD of 0.5, and a ratio of 0.15 will require 34 individuals in total (29 vs. 5) with 80% power and 0.05 type I error. We will, therefore, aim to recruit a total of 37 (31 vs. 6) participants for the study to allow for a dropout rate of 5%.

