4. OBJECTIVES AND OUTCOME MEASURES/ENDPOINTS

	Objectives	Outcome Measures
Primary	To develop and pilot test a novel MR imaging protocol with the aim to accurately: 1. Quantify tumour burden 2. Quantify bone loss	Novel imaging based endpoints: 1. DW-MRI: ADC change (Pawlyn et al, 2016) 2. Total spinal 'hole' volume 3. Total spine 'collapse' volume 4. FSA: trabecular wall thickness (Rafferty et al, 2016) Correlate endpoints: Bone density (DXA imaging) Serum CTX-1 Serum P1NP Further experimental serum biomarkers of myeloma bone disease
Secondary	To pilot test a novel MR imaging protocol with the aim to accurately: 1. Detect longitudinal changes in tumour load with therapy 2. Detect longitudinal changes in bone	1 and 2 - Repeat quantification of endpoint parameters after induction therapy and best response achieved by IWMG criteria or at treatment failure

microarchitecture with	3 – Analyse participants quality of
therapy	life using data from the EQ-5D-5L
3. Assess participants	questionnaire
Quality of Life (EQ-5D)	
throughout the study	
4. Assess participants experience of the novel MR imaging scan	4- Analyse participants experience of the novel MR imaging using data from MRI/DXA scanning questionnaire

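### Section 10.1 defines and sizes the primary outcome as follow-up ADC by response, but Section 10.2 plans no such comparison and Sections 1 and 4 list ADC change instead

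*Combined protocol and SAP*

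**What the plan says.** Section 10.1 defines the outcome: "The primary outcome of this study is the ADC in patients with and without a complete/very good partial response to therapy at follow-up". It assumes that "85% of individuals will reduce their myeloma burden from 40% to 10% or less compared with 15% who will achieve a partial response". It then sizes Group 1 for a difference "with an ADC in complete/ very good partial response of 1.5 at follow-up vs. 0.75 in those with a partial response", with an SD of 0.5, and concludes that this "will require 34 individuals in total (29 vs. 5) with 80% power and 0.05 type I error".

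Section 4, and the Synopsis in the same terms, lists the first imaging endpoint under the primary objective as "1. DW-MRI: ADC change". Response groups are not mentioned there. A secondary objective in the same table is "Detect longitudinal changes in tumour load with therapy".

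Section 10.2 sets out the analyses. Those that could involve ADC are a paired t test of the DW-MRI data between baseline and 6 months, correlations of the MR measures with bone density and bone markers, and ANOVA or ANCOVA of MR measures at follow-up between Group 1 and Group 2. The response categories appear once, to split Group 1 for the correlations.

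**The concern.** The definition, the endpoint list and the analysis section describe three different things. Section 10.1 fixes a time point (follow-up) and a contrast (with against without complete or very good partial response, CR/VGPR, in Group 1). Sections 1 and 4 name a different quantity and no contrast. Section 10.2 tests time, and disease group, but not response group.

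The contrast in 10.1 is the only one with a power calculation, and it sets the size of Group 1. If 10.2 is followed literally, that contrast is never estimated. If an analyst fills the gap later, the choice between follow-up value and change, adjusted or unadjusted, is open once the data are visible. With about 5 patients expected in the smaller group, that choice can matter.

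**Working it through.** **Inputs, all from Section 10.1.** Follow-up difference 1.5 − 0.75 = 0.75; SD 0.5; ratio 0.15; 29 vs. 5; alpha 0.05. In the cited study, for CR/VGPR, "the median ADC score improved from 0.79 (IQR 0.66 to 1.26) to 1.5" (follow-up IQR 0.88 to 1.83), and for partial response, "0.66 (IQR 0.52 to 0.87) to 0.75 (0.51 to 1.27) in those with a partial response". Two-sided testing is assumed because the sidedness is not stated. The correlation r between baseline and follow-up ADC is not in the documents and is varied from 0 to 0.75. Medians are treated as means, and normality is assumed.

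**1. The plan's own figure.** The noncentrality is δ / (SD × √(1/n₁ + 1/n₂)). With n₂ = 0.15 n₁, power is 79.2% at n₁ = 28 and 80.7% at n₁ = 29 (n₂ = 4.35, rounded up to 5). That gives 29 + 5 = 34, as stated. At exactly 29 vs. 5: 0.75 / (0.5 × 0.4842) = 3.098, critical t on 32 df = 2.037, power 85%. So the sizing matches a two-sample t test of follow-up ADC between response groups.

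**2. Section 10.2 against that contrast.**

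| Analysis in 10.2 | What it compares | Follow-up ADC by response? |
|---|---|---|
| Baseline characteristics | Groups 1, 2 and 3 | No |
| Paired t test | Baseline vs. 6 months | No response factor |
| Correlations | MR measures with bone density, CTX-1 and P1NP, within response strata and in Group 2 | No; association within a stratum, not a difference between strata |
| ANOVA / ANCOVA | Group 1 vs. Group 2 | No |
| EQ-5D regression, questionnaire summary | Not ADC | No |

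**3. Illustration: change between response groups.** No section plans this; it shows what would follow if the listed endpoint were joined to the sized contrast. Difference of median changes: (1.5 − 0.79) − (0.75 − 0.66) = 0.71 − 0.09 = 0.62. With SD 0.5 at each visit, the SD of change is 0.5 × √(2(1 − r)).

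A second scenario takes SD = IQR / 1.349. At follow-up this gives 0.704 and 0.563, pooled 0.688; at baseline 0.445 and 0.259, pooled 0.426. The SD of change is then √(0.688² + 0.426² − 2r × 0.688 × 0.426).

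| Power at 29 vs. 5 | r = 0 | 0.25 | 0.5 | 0.75 |
|---|---|---|---|---|
| Change, SD 0.5 (follow-up ADC: 85%) | 42% | 53% | 70% | 94% |
| Change, IQR-implied SDs (follow-up ADC: 59%) | 34% | 41% | 54% | 76% |

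**4. The test of change that is planned.** Mean change over 34 patients is (29 × 0.71 + 5 × 0.09) / 34 = 0.62. The worst case is r = 0. Adding the between-group part of the variance, (29 × 5 / 34²) × 0.62² = 0.048, the SD of change is √(0.500 + 0.048) = 0.74 at SD 0.5, or √(0.809² + 0.048) = 0.84 with IQR-implied SDs. Paired-test power is then about 99% or more in both scenarios.

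**5. Baseline-adjusted ANCOVA of the sized contrast.** The baseline medians differ by 0.79 − 0.66 = 0.13, so the adjusted difference is about 0.75 − slope × 0.13. With SD 0.5 at both visits the slope equals r, giving about 0.72, 0.69 and 0.65 at r = 0.25, 0.5 and 0.75. Simulated power at r = 0, 0.25, 0.5 and 0.75 is 84%, 83%, 87% and 97%, with a low of about 82% near r = 0.2. With IQR-implied SDs it is 57%, 54%, 56% and 72%. Because change is follow-up minus baseline, using it as the outcome lowers the baseline slope by 1 and leaves the response coefficient unchanged.

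**The case against.** Section 10.1 sits under a statistical methods heading and gives groups, time point, difference, SD and alpha, so a competent analyst can recover the intended test. That is fair as to intent, and step 1 confirms it. It does not settle the analysis: no test or adjustment is named, and the section that lists analyses omits it.

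It could also be said that the response wording in 10.2 implies the comparison. It does not, since correlating ADC with bone density inside each response group gives no estimate of how ADC differs between the groups.

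A stronger point concerns power. A reader might infer from step 3 that the study is underpowered for its listed endpoint. The documents do not support that. Sections 1 and 4 attach no response groups to ADC change, and the planned test of change is the paired t test, which is well powered on the same inputs. The 42% to 94% range belongs to a contrast that nobody has planned, and its width depends on the correlations assumed. Nor is the sample size arithmetic wrong.

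Finally, this is an observational pilot and the necessary scans are already planned. That bears on the ease of repair, not on the need for it.

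**Conclusion.** The point holds as a mismatch between definition, endpoint list and analysis plan. The only powered comparison, follow-up ADC by response in Group 1, has no analysis in Section 10.2, and Sections 1 and 4 name a different ADC quantity. This rests on the text alone and on no assumed figure.

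The numerical consequence is conditional. The sized comparison has 85% power at SD 0.5 (59% with IQR-implied SDs). If change between response groups were adopted instead, the corresponding ranges would be 42% to 94% and 34% to 76%, so the stated 80% could not be carried over without a justified correlation or SD of change.

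Two side points belong with the repair. First, the comparator is everyone without CR/VGPR in the definition but partial responders in the sizing. These coincide under the plan's 85% + 15% split and separate only if some patients do worse than partial response. Second, smouldering myeloma is in Group 1 in Section 6.1 but can be read as Group 2 in Section 7.1, and the plan does not say how an untreated Group 1 patient would be classed by response to therapy.

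**What to change.** Before analysis:

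- In Section 10.2, name the primary analysis as the two-sample comparison of follow-up ADC between Group 1 response groups that 10.1 sized, reported as a difference with 95% CI.
- Add ANCOVA of the same contrast with baseline ADC as covariate, as a stated supporting analysis. It serves readers of both definitions, since its response coefficient is the same for follow-up ADC and for change. It adjusts for measured baseline ADC only; the groups are not randomised.
- If ANCOVA is preferred as primary, restate the power in 10.1 for the adjusted target (about 82% to 97% at SD 0.5 for r from 0 to 0.75). Otherwise a new mismatch replaces the old one.
- Align Sections 1, 4 and 10.1 to one ADC endpoint definition and one comparator wording. Keep the paired t test for longitudinal change.
- Reconcile Sections 6.1 and 7.1 on smouldering myeloma, and state how untreated Group 1 patients enter the comparison. Leaving any out would reduce 29 vs. 5 by a number the documents do not give.

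The cost is wording, a little more analysis and one degree of freedom in the adjusted model. ADC is already planned at both visits, and 10.2 already uses baseline-adjusted ANCOVA for Group 1 against Group 2.

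### Section 10.1 enters cited medians as means; the quartiles beside them suggest a smaller mean ADC difference (about 0.47 to 0.56, not 0.75), so 80% power for a similar difference is not supported

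*Combined protocol and SAP*

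**What the plan says.** Section 10.1 defines the outcome that drives the sample size: "The primary outcome of this study is the ADC in patients with and without a complete/very good partial response to therapy at follow-up". It then summarises one earlier study. In patients with a complete or very good partial response (CR/VGPR), "the median ADC score improved from 0.79 (IQR 0.66 to 1.26) to 1.5 (IQR 0.88 to 1.83"). In partial responders (PR) the change was "0.66 (IQR 0.52 to 0.87) to 0.75 (0.51 to 1.27) in those with a partial response".

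The plan sets out to detect a difference like the one in that study, "with an ADC in complete/ very good partial response of 1.5 at follow-up vs. 0.75 in those with a partial response", with "a conservative estimated SD of 0.5" and a group ratio of 0.15. It arrives at 34 patients (29 vs. 5) for 80% power at a type I error of 0.05, and a recruitment aim of 37 (31 vs. 6) to cover 5% dropout. Sections 1, 5 and 6.1 give Group 1 as 34.

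Section 10.1 describes no conversion of medians to means and names no rank-based method. Section 10.2 adds only that endpoints will be checked for normality and transformed where possible.

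**The concern.** A difference and a common SD are the inputs for comparing two means. The 1.5 and 0.75 entered are medians. That substitution does little harm when distributions are roughly symmetric, but the quoted quartiles are not symmetric, and the asymmetry runs in opposite directions:

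- CR/VGPR: 1.5 − 0.88 = 0.62 below the median and 1.83 − 1.5 = 0.33 above. The mean probably lies below 1.5.
- PR: 0.75 − 0.51 = 0.24 below the median and 1.27 − 0.75 = 0.52 above. The mean probably lies above 0.75.

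Both shifts shrink the difference in means. If so, the stated power does not apply to the effect seen in the study it is taken from, on the scale the formula uses. This is the comparison Section 10.1 calls primary, and one group is expected to hold about five patients. A reader who trusts the 80% could give a non-significant result more weight than it can bear.

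**Working it through.** **Inputs (all from Section 10.1).** Follow-up median and quartiles: CR/VGPR 1.5 (0.88, 1.83); PR 0.75 (0.51, 1.27). SD 0.5; ratio 0.15; alpha 0.05; power 80%; 29 vs. 5, with 31 vs. 6 to be recruited. Sidedness is not stated. Two-sided is assumed because it reproduces the plan's figure.

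**Step 1: reproduce the plan.** Two-sample t-test, noncentral t, difference 0.75, SD 0.5, ratio 0.15, 80% power: n1 = 28.52 and n2 = 0.15 × 28.52 = 4.28. Rounding each up gives 29 + 5 = 34, an exact match. One-sided gives 22 + 4 by the normal approximation, which does not match. So this is a comparison of means with 1.5 and 0.75 entered as the means.

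**Step 2: power at the plan's own inputs.** Noncentrality = difference / (SD × √(1/29 + 1/5)), and √(1/29 + 1/5) = 0.484. For 0.75: 0.75 / (0.5 × 0.484) = 3.10 on 32 degrees of freedom, power 85.2%. It exceeds 80% because both groups were rounded up, so 85% is the fair baseline.

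**Step 3: estimate the means from the quartiles.**

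| Estimator | CR/VGPR | PR | Difference |
|---|---|---|---|
| (Q1 + median + Q3)/3 | 4.21/3 = 1.403 | 2.53/3 = 0.843 | 0.56 |
| Weighted: w(Q1 + Q3)/2 + (1 − w) × median, w = 0.7 + 0.39/n | about 1.40 | about 0.85 | 0.54 to 0.55 (n from 10 to 1000) |
| (Q1 + Q3)/2 | 2.71/2 = 1.355 | 1.78/2 = 0.89 | 0.465 |

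The source group sizes n are not in the documents, so the weighted estimator is shown over a range.

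**Step 4: power at those differences, SD 0.5, two-sided t.**

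| Mean difference | 29 vs. 5 | 31 vs. 6, no dropout |
|---|---|---|
| 0.75 | 85.2% | 90.5% |
| 0.56 | 61.1% | 68.5% |
| 0.545 | 58.8% | 66.1% |
| 0.465 | 46.1% | 52.7% |

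Solving for 80% at 29 vs. 5 and SD 0.5 gives a mean difference of 0.70.

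**Step 5: the same quartiles also bear on the SD.** IQR/1.349 gives (1.83 − 0.88)/1.349 = 0.70 for CR/VGPR and (1.27 − 0.51)/1.349 = 0.56 for PR. Simulating normal data with these SDs at 29 vs. 5 gives power of about 60% at 0.75 and about 35% at 0.56.

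**Step 6: range over both inputs, 29 vs. 5, common SD.**

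| Mean difference | SD 0.5 | SD 0.6 | SD 0.7 |
|---|---|---|---|
| 0.75 | 85% | 71% | 57% |
| 0.56 | 61% | 46% | 36% |
| 0.465 | 46% | 34% | 27% |

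**The case against.** **The arithmetic is right.** Section 10.1 states its inputs openly, 29 vs. 5 follows from them, and power at those inputs is 85%. This stands. The point concerns a planning assumption, not a miscalculation.

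**Quartiles do not fix a mean.** This also stands. Suppose ADC lay between 0 and 2.5 (an assumption). The quoted quartiles would then allow a CR/VGPR mean from (0 + 0.88 + 1.5 + 1.83)/4 = 1.05 to (0.88 + 1.5 + 1.83 + 2.5)/4 = 1.68. For PR the limits are (0 + 0.51 + 0.75 + 1.27)/4 = 0.63 and (0.51 + 0.75 + 1.27 + 2.5)/4 = 1.26. The difference could run from about −0.2 to 1.05, which includes 0.75. A reader might infer that the true mean difference is 0.56 and the true power 61%. The documents do not support that: 0.56 is one estimator's value, and the estimators tried span 0.47 to 0.56.

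**The asymmetry could be sampling noise.** If the source groups had about 10 patients each (an assumption), a normal distribution would show asymmetry at least this large in the stated direction in about 21% (CR/VGPR) and 16% (PR) of samples. At 30 each the figures are about 10% and 6%. So skewness is not established. But sampling error affects the medians too, so this does not restore 0.75 as the mean difference.

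**61% at SD 0.5 mixes two sources.** It takes the means from the quartiles but leaves the SD at the plan's value, although the same quartiles point to a larger SD. This stands, and it is why the fix asks for a range over both inputs.

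**It is a pilot.** True, and the documents do not say how a null result would be read. But Section 10.1 still makes a specific power claim for its primary outcome, and nothing elsewhere repairs it. A normality check and possible transformation at analysis do not change the planning inputs.

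**Conclusion.** The concern holds as a moderate one. Section 10.1 uses medians as means, and the quartiles printed beside them suggest a mean difference of roughly 0.47 to 0.56 instead of 0.75. At 29 vs. 5 and SD 0.5, power falls from about 85% to about 46% to 61%. At 31 vs. 6 with no dropout it falls from about 90% to about 53% to 69%. With the SDs the same quartiles suggest, power at 29 vs. 5 is about 60% at 0.75 and about 35% at 0.56. The 80% claim for a difference similar to the cited one is therefore not supported by the figures cited for it.

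This rests on a two-sided t-test, on conventional quartile-based estimators of mean and SD, and on source groups of unknown size. The direction is the same for all three estimators of the mean; the exact size is uncertain.

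A reader might go further and infer that the sample size is miscalculated, or that the study cannot proceed as sized. Neither follows: the stated number reproduces exactly, and correcting the stated power changes no patient number, procedure or planned analysis in an observational pilot.

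**What to change.** In Section 10.1:

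1. State that 29 vs. 5 gives 80% power only for a mean ADC difference of 0.70 or more at SD 0.5 (two-sided t-test).
2. Remove the claim that a difference similar to the cited study is covered at 80%.
3. Add a short power range over the mean difference (about 0.47 to 0.75) and the SD (0.5 to about 0.7), as in the last table of the working. Note that the cited values are medians and that the means and SDs are estimated from quartiles. Do not print a single replacement figure such as 61%.

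In Section 10.2, report the difference in follow-up ADC between response groups with its confidence interval, so that a non-significant result is read against its precision. A rank-based comparison alongside is optional.

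The cost is a few sentences and one small table, with no extra patients or scans. The downside is that the stated power becomes less favourable.

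### The SD of 0.5 behind the Group 1 sample size is below both SDs implied by the follow-up IQRs the plan quotes, so 29 vs. 5 patients give about 60% power, not 80%

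*Combined protocol and SAP*

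**What the plan says.** Section 10.1 of the combined protocol and SAP defines the endpoint: "The primary outcome of this study is the ADC in patients with and without a complete/very good partial response to therapy at follow-up". It then cites an earlier study in a similar population. In responders the "median ADC score improved from 0.79 (IQR 0.66 to 1.26) to 1.5 (IQR 0.88 to 1.83"); in partial responders the figures were "0.66 (IQR 0.52 to 0.87) to 0.75 (0.51 to 1.27) in those with a partial response".

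The next paragraph carries the follow-up medians into the calculation, as an "ADC in complete/ very good partial response of 1.5 at follow-up vs. 0.75 in those with a partial response". It does not carry over the follow-up spread. It says instead that "a conservative estimated SD of 0.5, and a ratio of 0.15 will require 34 individuals in total (29 vs. 5) with 80% power", at a type I error of 0.05. The one SD serves both groups, and no derivation is given. The total is raised to 37 (31 vs. 6) for 5% dropout. The Synopsis and sections 5 and 6.1 plan 34 patients in Group 1.

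**The concern.** The effect size and the spread should describe the same quantity. Here the effect comes from the earlier study's follow-up values, while the SD is smaller than that study's own follow-up spread. The error lies in the direction that makes the sample look sufficient, although the text calls the choice conservative.

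This calculation is the only justification given for the size of Group 1. A reader of a non-significant primary comparison would take the chance of having missed the planned difference to be 20%. On the quoted data it is about 40%.

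**Working it through.** **Inputs, all from section 10.1.** Difference 1.5 − 0.75 = 0.75; SD 0.5; ratio 0.15; 80% power; alpha 0.05; follow-up IQRs 0.88 to 1.83 and 0.51 to 1.27. Sidedness is not stated. Two-sided is assumed because it reproduces the plan's number.

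**Step 1: reproduce the plan.** For a two-sample t-test with n2 = 0.15 × n1, the noncentral t gives 80% power at n1 = 28.5 and n2 = 4.3. Rounding each up gives 29 + 5 = 34, as stated. Dropout: 29/0.95 = 30.5, rounded up to 31, and 5/0.95 = 5.3, rounded up to 6; total 37, as stated. The method is therefore identified, and the plan's arithmetic is right for its inputs. Because of the rounding up, 29 vs. 5 has 85.2% power at SD 0.5.

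**Step 2: SDs implied by the IQRs.** For a normal distribution, SD = IQR width / 1.349.

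- Complete or very good partial response: (1.83 − 0.88)/1.349 = 0.95/1.349 = 0.704
- Partial response: (1.27 − 0.51)/1.349 = 0.76/1.349 = 0.563
- Pooled at 29 vs. 5: √[(28 × 0.704² + 4 × 0.563²)/32] = 0.688

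**Step 3: power at 29 vs. 5 for a difference of 0.75.** The noncentrality is 0.75 / [SD × √(1/29 + 1/5)], with 32 degrees of freedom. At SD 0.5 it is 0.75/0.242 = 3.10; at SD 0.688 it is 0.75/0.333 = 2.25.

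| SD used | Power, 29 vs. 5 | Power, 31 vs. 6 |
|---|---|---|
| 0.5 in both groups (the plan) | 85.2% | 90.5% |
| 0.563 in both groups | 76.0% | 82.7% |
| 0.638 (unweighted average of the variances) | 65.4% | 72.7% |
| 0.688 (weighted pooled) | 58.8% | 66.1% |
| 0.704 in both groups | 56.9% | 64.1% |
| 0.704 and 0.563, simulated, pooled t-test | 60% | 69% |
| 0.704 and 0.563, simulated, Welch test | 61% | 71% |

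**Step 4: what 29 vs. 5 can support.** The largest common SD that keeps 80% power for 0.75 is 0.536, below both implied SDs. The difference detectable with 80% power is 0.70 at SD 0.5 and 0.96 at SD 0.688.

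**Step 5: size needed for 80% power at 0.75, SD 0.688.** 48 vs. 8 (56 patients) gives 80.0%, at a ratio of 8/48 = 0.167. Keeping the plan's ratio of 0.15 and its rounding gives n1 = 52.4 and n2 = 7.9, so 53 + 8 = 61. The normal approximation gives 51 + 8 = 59.

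**The case against.** **The conversion from IQR to SD assumes normality, and the quoted quartiles are asymmetric.** This stands as a limit on precision: 0.70 and 0.56 are approximate, and the documents do not say how many patients lie behind them. It does not rescue the 80%. The plan's calculation is itself a normal-theory comparison of means, and these IQRs are its only information on follow-up spread. The asymmetry also points the wrong way for the plan. The longer tail is downward in responders and upward in partial responders, so the difference in means is probably below 0.75. As a rough sensitivity figure only, averaging each group's three quartiles gives 1.40 − 0.84 = 0.56, and about 37% power at SD 0.688. Section 10.2 allows transformation, but the sample size does not use it.

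**The value 0.5 may summarise all four quoted IQRs.** The baseline IQRs imply SDs of 0.445 and 0.259, and the four SDs average about 0.49. That may be its origin, but the text does not say so. The comparison is at follow-up, and an average over both time points is not a cautious choice for it.

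**Baseline adjustment could reduce the residual SD.** It could, but section 10.1 does not invoke it and no baseline-to-follow-up correlation is given. The ANCOVA in section 10.2 compares Groups 1 and 2, not the response categories.

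**A favourable combination reaches higher power.** At 29 vs. 5, a large-sample unequal-variance formula gives 75%, but it ignores that one group has five patients; the simulated Welch test gives 61%. The normal approximation with SD 0.563 in both groups gives 78.5%. At 31 vs. 6 with no dropout, that smaller SD in both groups exceeds 80% (82.7%), but this assigns the partial responders' spread to the 31 responders.

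**This is a pilot.** That is a reason to present an estimate with its uncertainty, and the remedy can be confined to wording. It is not a reason to keep a power figure that the quoted data contradict.

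**Conclusion.** The concern holds. The fault is the SD and its description as conservative; the arithmetic that follows from it is correct. On the plan's own quoted follow-up data, 29 vs. 5 has about 60% power for a difference of 0.75. All variants examined at that size fall below 80%: 57% to 76% by the t-test and simulation, and at most 78.5% by the normal approximation. Enrolling 31 vs. 6 with no dropout gives about 66% to 71% when both implied SDs are used.

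The conclusion assumes a two-sided test, approximate normality in converting IQRs to SDs, and a true difference as large as the difference in medians. If the difference in means is smaller, power is lower still.

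**What to change.** In section 10.1:

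- Delete the word conservative and replace SD 0.5 with the SDs implied by the quoted follow-up IQRs, about 0.70 and 0.56, showing the conversion and its normality assumption.
- Restate the design property: 29 vs. 5 gives about 60% power for a difference of 0.75 (57% to 76% depending on how the SDs are combined), or 80% power for a difference of about 0.96.
- State that the primary comparison will be reported as a pilot estimate with a 95% confidence interval.

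The cost is a rewording and a less favourable stated power; no patients or procedures are added. If the sponsor prefers to keep 80% power for 0.75, Group 1 would need about 56 to 61 evaluable patients, depending on the ratio and the rounding.
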